9.3 CAMPUS TRIAL STATISTICAL ANALYSES

9.3.1 GENERAL APPROACH

Overview and Intent-to-Treat. The proposed trial design of adaptive treatment strategies (ATSSs) is like a factorial design;^{156,157,158,159} different analytic subgroups (see Table 8) are combined to answer different questions. Aim 1 is the trial's primary aim; Aims 2-5 are secondary aims and Aim 6 as an implementation aim. All student participants, once randomized, will be included in the intent-to-treat sample, and every effort will be made to collect all primary and secondary outcomes even if a student participant does not engage in randomly assigned treatments. The primary outcome of interest is suicidal risk, which includes suicidal ideation as well as suicide-related behaviors, such as non-suicidal self-injury (NSSI) and suicide attempts (SAs); however suicidal ideation is the primary DV due to relatively low rates of suicidal behaviors post-baseline with college students. Suicides will be tallied as well. All analyses allow for the inclusion of covariates listed as demographics and covariates in Section 8.1. Covariates will enter the model based in clinical importance (gender, age, current alcohol use, current substance use, etc.) and retained on a case-by-case basis based on statistical significance.

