6.1.4 RANDOMIZATION

Following the completion of the baseline assessment, the site PC will review the consent, document the randomization block variables (gender, medication, past suicide attempt), obtain randomization assignment from the Data Center at Duke University, and reveal randomization results to an already assigned counselor. Note that student participants will learn of their treatment assignment by the counselor at their first treatment visit (this procedure was used in the pilot project and received very favorably by students and counselors).

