6.3 MEASURES TO MINIMIZE BIAS: RANDOMIZATION AND BLINDING

Randomization

We will rely on an adaptive-biased coin design¹⁰⁹ to attempt to balance conditions at each stage based on gender, previous suicide attempt(s), and current psychotropic medications. At Stage 2, the PC will obtain information on the blocking variables, along with the tailoring variable, from counselors and the electronic medical record (EMR; Titanium for all sites) prior to randomization. The PC at each site will randomize subjects via the centralized database using a customized system tailored for the SMART design housed at the Duke Data Center.

All assessments of the main endpoints will be performed by the independent evaluators (IEs), who will remain blind to treatment status. It is always possible that student participants could tell the IE during their assessments about the type of therapy they have been receiving. To mitigate this risk, all student participants will be reminded about the importance of not telling the IEs which treatment they received. It is also possible that counselor participants could tell the IE which treatment condition a particular student participant is in; counselor participants will be frequently reminded not to do so. To evaluate how well blinding was maintained, the IEs will be asked to indicate what treatment group(s) they thought the student participant belonged to at the end of stage 1 and, if applicable, at the end of stage 2.

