6.5 CONCOMITANT THERAPY

If it is discovered during or after the study that a participant received a “crossover-treatment” on his/her own or received any other form of therapy, we will document these treatments in the clinical record and on the treatment history form that is completed by the student participant and the IE and develop procedures to minimize this threat as much as possible for use in the large-scale trial.

While clinical and research staff are expected to strongly discourage treatment outside the study, these student participants will continue to be treated within their assigned treatment arm. Stated differently, student participants receiving non-protocol treatments on their own accord are not automatically considered premature terminators. On the other hand, student participant-initiated crossover treatments should prompt consideration of a review of the student participant’s clinical status. An example of this would be the case of a student participant-initiated psychiatric hospitalization for worsening depression, which would automatically lead to premature termination.

Handling of Medications. Student participants will neither be asked to discontinue medications or to start medications as part of the study. Following regular CCC practice, student participants may be referred for a psychiatric consultation if needed. We will stratify on current use of psychotropic medication at both randomization points to equate medication use across

conditions. We will also assess for any mid-treatment use of medications via data collected on the treatment history interview. Approximately a quarter of students presenting to a CCC are already on a psychiatric medication.⁴² This approach to medication reaches a good balance of allowing for medications while not including an active protocol on psychotropic management and it seems appropriate, given the limited evidence of pharmacotherapy-only treatment for SR.¹⁴⁸

7 STUDY INTERVENTION/EXPERIMENTAL MANIPULATION DISCONTINUATION AND PARTICIPANT DISCONTINUATION/WITHDRAWAL

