8 STUDY ASSESSMENTS AND PROCEDURES

8.1 ENDPOINT AND OTHER NON-SAFETY ASSESSMENTS

We have divided measures into demographics, primary and secondary dependent variables (DVs), mediators, moderators, and implementation/process variables. Measures were selected if they: 1) fit the study aims, 2) have adequate psychometrics, 3) are listed as Common Data Elements in NIH or have been used in previous SR studies, 4) have shown sensitivity to change, 5) have been used with college students, 6) map onto the RDoC categories (Negative Valence Systems, Positive Valence Systems, Cognitive Systems, Social Processes, and Arousal and Regulatory Systems),⁷⁹ 7) are directly relevant to the application of CAMS or DBT, and 8) allow for reduced burden to student participants—the latter in response to reviewers' concerns.

Demographic Variables.

With student participants' consent, age, marital status, family income, residence, GPA, race, year in school, major, ethnicity, sexual orientation, cultural identity, and gender identity will be obtained via EMR/the registrar or by completing the Demographic Information Form at baseline.

SMART Primary Tailoring Variable: Sufficient vs. Insufficient Response to Stage 1 Treatments. Unique to SMARTs are tailoring variables or variables upon which subsequent randomizations are based.⁵⁹ For this trial, sufficient treatment response will be the primary tailoring variable and assessed by the Clinical Global Impressions (CGI),¹⁰³ adapted to SR. As noted in Preliminary

Studies, the CGI, adapted to SR, showed high inter-rater reliability and construct validity; this fits with other studies demonstrating that non-blinded trained counselors typically can offer CGI ratings commensurate to blinded IEs.¹¹¹

In SMARTs, a tailoring variable is a tool for clinical decision-making, in this case deciding on response to treatment, and therefore it will be based on clinical assessments by providers (and not the IE).⁵⁹ Beginning at session 4 and following each subsequent session, the counselor will complete the 7-point Likert-style CGI developed in the CAMPUS feasibility study to rate overall improvement in SR since baseline from (1) “*Very much improved*” to (7) “*Very much worse*.” Sufficient response will be defined as an Improvement score of ≤ 2 (“*Much improved*” or “*Very much improved*”).

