A student participant in Stage 1 showing significant worsening may be re-randomized to Stage 2 conditions earlier. Similarly, students who begin the study with significant suicidality and show no improvement after 4 sessions may also be considered for early randomization to Stage 2.

Primary DV: Suicide-Related Behaviors – Relevant to Aims 1, 2, and 3.

Recognizing that measurement of suicide-related behaviors is fraught with challenges,¹¹² we are defining SR as “suicidal ideation, attitudes, behaviors and plans which take into account severity, intent, and ability to cope with ideation without engaging in suicidal behaviors, such as planning/rehearsal, NSSI, suicide attempts (SAs), and suicide.” Our primary assessment measures for SR are two interviews to measure suicidal ideation (SI; defined as self-reported thoughts of suicide-related behavior) and suicidal behaviors, including suicide attempts and non-suicidal self-injury (NSSI). Suicides will also be tallied.

- 1) The Scale for Suicide Ideation—Current (SSI)^{99,113} is a 19-question interview that assesses the student participant’s highest SI in the past 2 weeks, including attitudes, behaviors, and plans. Each item is rated as 0,1, or 2 with a total scale of 0-38. The IEs will be trained and certified on the SSI.
- 2) The Self-Injurious Thoughts and Behaviors Interview (SITBI)¹¹⁴ is a 3-15-minute interview containing modules that assess SI, suicide plans, suicide gestures, suicide attempts, and NSSI. The SITBI has been used with college students.^{115,116} The IEs will be trained and certified on the SITBI.

Secondary DVs/Covariates: Functioning – Relevant to All Aims

- 1) The CCAPS-34¹⁰⁷ assesses key domains of college student mental health (Depression, Generalized Anxiety, Social Anxiety, Academic Distress, Eating Concerns, Substance Use, and Hostility/Anger) and an overall Distress Index score. Students respond to questions using a 5-point rating scale (“*not at all like me*” to “*extremely like me*”). The CCAPS-34 takes only 2-3 minutes to complete¹⁰⁷ and is widely used in CCCs.²²¹ The CCAPS will be assessed at all assessment points and at every session. The question on SI will screen prospective participants and the weekly administration can track SI fluctuations more frequently.

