Aim 2 analyses will contrast ATSSs beginning with CAMS vs. interventions beginning with TAU (i.e., to evaluate the main effect of initial treatment) on change (decrease) in suicide-related risk behaviors (SI, NSSI, and suicide attempts—the primary outcomes) from baseline to the end of Stage 2 (the primary contrast). This is a comparison of cells A+B+C vs. D+E+F (see Figure 2 and Table 8). Note that the primary continuous longitudinal outcome is assessed at baseline, mid-Stage 1 (3 weeks), post Stage 1 (6 weeks), mid-Stage 2 (10 weeks), post-Stage 2 (14 weeks) (end of acute treatment) and then again at 3-month follow-up (26 weeks), for a total of 6 measurement occasions. Linear mixed models¹⁶³ (LMM, also known as random effects or growth curve models), fit with SAS PROC MIXED will be used to analyze the longitudinal data. LMMs use all available measurements, allowing student participants to have an unequal number of observations and producing unbiased parameter estimates as long as unobserved values are missing at random. The analysis will fit a LMM with fixed effects for the intercept, time, group, and a group-by-time interaction term, where group is an indicator of phase-one treatment (CAMS vs. TAU as referent). The LMM will also include random effects for the intercept and time and an unstructured within-person correlation structure for the residual errors and will adjust for the following measures collected at baseline (pre-randomization): site, age, race, and clinical severity. Model diagnostics will be used to determine suitability of more parsimonious (e.g., autoregressive) correlation structures, and nonlinear (e.g., quadratic) effects for time. We do not expect the intervention effects to be attenuated due to counselor participants who are cross classified between the interventions. Nonetheless, we will assess the potential attenuation by assessing the counselor x intervention interaction. If significant, we will examine if the attenuation effect is limited to a select few counselors and eliminate as needed to remove potential counselor contamination of intervention effects. Counselor will be treated as a random effect which models potential correlation between student participants within a common counselor. If there is not sufficient variance, indicated by the reliability estimate of the random effect falling below 0.02 (a slighter lower threshold compared to

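### Aim 1 has no prespecified covariate set: covariates are kept on significance with no threshold, and two of the three randomisation balancing factors are on no covariate list

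*Combined protocol and SAP*

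**What the plan says.** Section 9.3.1 makes Aim 1 the primary aim and gives the only covariate rule that reaches it: "All analyses allow for the inclusion of covariates listed as demographics and covariates in Section 8.1". Entry is by clinical importance, illustrated by gender, age, and present alcohol and drug use, and the examples do not close the list. Covariates are then "retained on a case-by-case basis based on statistical significance". No p-value, test or time of decision is given.

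The Section 8.1 pool has two parts. The demographics are "age, marital status, family income, residence, GPA, race, year in school, major, ethnicity, sexual orientation, cultural identity, and gender identity". The second part is headed "Secondary DVs/Covariates: Functioning" and holds the CCAPS-34, the CGI scales and academic functioning.

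Section 9.3.2 describes Aim 1 as a weighted comparison of the four strategies using the known randomisation probabilities, and names no covariate. The Aim 2 model, by contrast, "will adjust for the following measures collected at baseline (pre-randomization): site, age, race, and clinical severity". Aim 3 takes over that model by reference, and Aim 8 (9.3.7) repeats the same four for both stages.

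Section 6.3 says that allocation will "attempt to balance conditions at each stage based on gender, previous suicide attempt(s), and current psychotropic medications"; Section 6.1.4 names the same three factors. Section 6.5 adds: "We will stratify on current use of psychotropic medication at both randomization points".

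**The concern.** Two separate matters arise.

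**Selection.** A secondary aim has a named set of pre-randomisation covariates; the primary aim has a pool and a discretionary rule. Several adjusted models for the same contrast could be defended once outcomes are known. Hypothesis 1 claims that one strategy is superior, and 9.3.2 plans contrasts to show whether any is clearly better or worse, so the choice could matter for inference. Nothing in 9.3.1 restricts covariates to baseline either. The 8.1 covariate heading includes CGI-I, which rates change since baseline and so exists only after randomisation. Because the rule covers all analyses, it is also unclear whether the fixed list for Aims 2, 3 and 8 may be extended or pruned.

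**Balancing factors.** When allocation is balanced on prognostic factors and the analysis ignores them, the reported standard error does not reflect the balance achieved.

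**Working it through.** **Step 1. Factors against lists.**

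| Factor balanced at both stages | 9.3.1 examples | 8.1 demographics or covariates | Fixed list, Aims 2, 3, 8 |
|---|---|---|---|
| Gender | yes | yes (gender identity) | no |
| Previous suicide attempt | no | no | no |
| Psychotropic medication | no | no | no |

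Previous attempts otherwise enter the analysis only as an Aim 5 moderator or predictor (8.1, 9.3.3).

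**Step 2. The plan's own figures.** None depends on covariates. Aim 2 power with 240 per arm, d = 0.30 and two-sided 2.5% is Φ(0.30 × √(240/2) − 2.241) = Φ(1.045) = 85.2%, which matches the stated 85%. Aim 1 is sized on a 90% probability of picking the best strategy, not on a test.

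**Step 3. Assumptions for the simulations.** The documents give no covariate strengths, so R² of 2%, 5%, 10% and 15% of week-14 SSI variance is assumed; results below are in that order.

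- From the documents: N = 480, 60% female (5.4), about a quarter on medication (6.5), 50% response (4.2).
- Assumed: 30% with a previous attempt, two-level gender, correlation −0.3 between latent response and outcome, no missing data, balance by blocking within the eight strata.
- The estimator is a reconstruction. Responders are weighted 1/0.5 = 2 and counted in both compatible strategies; non-responders are weighted 1/(0.5 × 0.5) = 4; the robust standard error is clustered by participant.
- The contrast is ATS-2 against ATS-4, with the four covariates that 9.3.1 names. The 2.5% level is the one that 9.2 uses for Aims 2 and 3; none is stated for Aim 1.

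**Step 4. Selection.**

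| | R² 2% | 5% | 10% | 15% |
|---|---|---|---|---|
| False positives, all four fixed | 2.7% | 2.4% | 2.3% | 2.3% |
| False positives, most favourable of five cut-offs (0.01, 0.025, 0.05, 0.10, 0.20) | 3.1% | 2.7% | 2.4% | 2.3% |
| Verdict depends on the cut-off, true gap 0.25 SD | 3.4% | 3.5% | 1.4% | 0.2% |
| Upper bound: false positives, best of all 16 subsets | 3.1% | 3.1% | 3.7% | 4.6% |
| Upper bound: verdict depends on the subset, true gap 0.25 SD | 7% | 12% | 17% | 20% |

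Monte Carlo error on the false-positive rates is about 0.2 points. The upper-bound rows come from a separate run, so differences of that size between rows mean nothing. A single mechanical p < 0.05 rule gives 2.2-2.7%, the same range as the fixed set in that run. Freedom over the cut-off matters less as R² grows, because strong covariates are then almost always kept: about 95% of the time at R² 10% and over 99% at 15%, for p < 0.05.

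**Step 5. Omitting the balanced factors.** With exact balance, the unadjusted standard error is too large by 1/√(1 − R²) − 1 = 1.0%, 2.6%, 5.4%, 8.5%. Simulated Aim 1 standard errors (SD units) without and with the factors agree to rounding: 0.1119/0.1107, 0.1117/0.1089, 0.1118/0.1061, 0.1118/0.1030. The true spread of the estimate is the same either way (ratio 1.000-1.003), so all of this is overstatement. The actual level of a nominal 2.5% test is 2 × [1 − Φ(2.241/√(1 − R²))] = 2.4%, 2.1%, 1.8%, 1.5%.

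With no balancing at all, the excess would be real loss of precision rather than overstatement. The biased coin lies between, so the 1.0-8.5% is an upper bound on overstatement.

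With the best strategy 0.25 SD ahead, it is picked in 98-99% of simulated trials with or without the factors.

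**The case against.** The strongest reply has four parts.

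- **The rule is harmless.** Retention on a covariate's own p-value hardly moves the false-positive rate. This stands. A reader might infer that the rule itself produces 3-5% false positives or a verdict that turns on the model in 7-20% of trials. It does not: those rows require choosing any subset with the treatment result in view, including subsets that drop covariates the rule would keep. They bound what unrestricted discretion could do. The cut-off rows, for their part, do not test discretion over which covariates enter or a different cut-off for each.
- **The list is not open.** This also stands: 9.3.1 points to a finite pool in 8.1. What is unspecified is entry and retention within it. The edge is also blurred, because 9.3.1 cites alcohol and drug use while 8.1 files the AUDIT and DAST as moderators.
- **Aim 1 may be unadjusted.** That is a fair reading of permissive wording in 9.3.1 and silence in 9.3.2, but the plan does not say so.
- **Omitting balanced factors is safe.** A reader might infer bias or a weakened design. Neither follows: randomisation protects the estimate, the error is conservative, and the sizing figures for Aims 1 and 2 contain no covariate term.

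The undefined clinical severity covariate might be read as touching previous attempts, but it does not name them or medication, and it is not part of the Aim 1 text.

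**Conclusion.** The gap is real and modest. The primary aim lacks a prespecified covariate set, and the analysis does not follow the factors used in allocation. Under assumed R² of 2-15%, freedom over the retention cut-off puts the false-positive rate at about 2-3% for a 2.5% test and changes the verdict in about 3.5% of trials or fewer. Omission of the balanced factors overstates the Aim 1 standard error by at most about 1-8.5% and leaves the 90% selection criterion unaffected. These sizes rest on assumed covariate strengths, a reconstructed estimator and complete data. The reason to act is that a fixed set is better than the stated rule and needs no new data, not that the trial's conclusions are in danger.

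**What to change.** In 9.3.1, delete retention by statistical significance. State one fixed set of pre-randomisation covariates for Aim 1: gender, previous suicide attempt (yes/no), current psychotropic medication, site, age, race and baseline SSI. Add the three balancing factors to the Aim 2, 3 and 8 models, using the values recorded at Stage 2 randomisation in Stage 2-only models. Report any other covariate as a sensitivity analysis. Say in advance how sparse categories are collapsed: Section 5.4 predicts 2% transgender or non-binary (0.02 × 480 ≈ 10 students) and two race categories at 1% or less (at most about 5 each).

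The cost is wording, since the factors are already recorded before each randomisation. Aim 1 uses about 13 degrees of freedom: site 3, age 1, race up to 5, baseline SSI 1, factors 3. Race has six categories because Sections 5.4 and 8.1 record ethnicity separately. If nothing were prognostic, the simulated standard error rises by 0.6% with 12 degrees of freedom and 0.8% with 14, so under 1% with 13. If baseline SSI correlates 0.3 or 0.4 with week 14 (assumed; 9.2 gives such values only for later visits) and the factors explain 2%, it falls by about 5% or 9%. The Aim 2, 3 and 8 models gain 3 degrees of freedom, or 4 if gender keeps three levels.

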9.3.2 ANALYSIS OF THE PRIMARY ENDPOINT(S)

Aim 1 analyses (Primary Aim) will compare and contrast the 4 pre-specified ATSSs embedded in the SMART design to determine whether one is clearly better or worse than the others with respect to mean suicidal ideation (SI) and suicide-related behaviors (NSSI and suicide attempts), which are the primary outcomes, at the end of 14 weeks of treatment. The data analysis method of Robins and colleagues^{160,161} will be used to contrast the 4 ATSSs based on reducing

suicide-related risk behaviors (SI, NSSI, and suicide attempts) to determine whether any of the interventions appear to be clearly better or worse than others. As part of the design, a student participant will contribute differentially to one or more of the 4 strategies (depending on the treatments to which he or she is randomized and whether he or she is a treatment responder), requiring a weighted comparison. Specifically, this analysis involves a weighted comparison of the cells A+B vs. A+C vs. D+E vs. D+F (see Table 8); the method by Robins and colleagues^{160,161} weights each student participant using the known randomization probabilities. Linear contrasts among the components of the ATSSs will be performed to further understand impact on efficacy. Similar analyses will compare the 4 strategies on the follow-up and secondary outcomes outlined above. Additionally, in response to reviewers' input, a composite outcome including suicidal ideation, suicide attempts, and NSSI will be derived. Death by suicide will be tallied but not included in the composite score. Song and colleagues¹⁶² provide a thorough discussion of the best ways to create composite scores, especially when dealing with a mixture of continuous and count outcomes. The analysis team will determine the best approach in the formation/derivation of the composite using the steps discussed by Song et al¹⁶². Similar analyses will compare the 4 strategies on the derived composite as outlined above.

Aim 2 analyses will contrast ATSSs beginning with CAMS vs. interventions beginning with TAU (i.e., to evaluate the main effect of initial treatment) on change (decrease) in suicide-related risk behaviors (SI, NSSI, and suicide attempts—the primary outcomes) from baseline to the end of Stage 2 (the primary contrast). This is a comparison of cells A+B+C vs. D+E+F (see Figure 2 and Table 8). Note that the primary continuous longitudinal outcome is assessed at baseline, mid-Stage 1 (3 weeks), post Stage 1 (6 weeks), mid-Stage 2 (10 weeks), post-Stage 2 (14 weeks) (end of acute treatment) and then again at 3-month follow-up (26 weeks), for a total of 6 measurement occasions. Linear mixed models¹⁶³ (LMM, also known as random effects or growth curve models), fit with SAS PROC MIXED will be used to analyze the longitudinal data. LMMs use all available measurements, allowing student participants to have an unequal number of observations and producing unbiased parameter estimates as long as unobserved values are missing at random. The analysis will fit a LMM with fixed effects for the intercept, time, group, and a group-by-time interaction term, where group is an indicator of phase-one treatment (CAMS vs. TAU as referent). The LMM will also include random effects for the intercept and time and an unstructured within-person correlation structure for the residual errors and will adjust for the following measures collected at baseline (pre-randomization): site, age, race, and clinical severity. Model diagnostics will be used to determine suitability of more parsimonious (e.g., autoregressive) correlation structures, and nonlinear (e.g., quadratic) effects for time. We do not expect the intervention effects to be attenuated due to counselor participants who are cross classified between the interventions. Nonetheless, we will assess the potential attenuation by assessing the counselor x intervention interaction. If significant, we will examine if the attenuation effect is limited to a select few counselors and eliminate as needed to remove potential counselor contamination of intervention effects. Counselor will be treated as a random effect which models potential correlation between student participants within a common counselor. If there is not sufficient variance, indicated by the reliability estimate of the random effect falling below 0.02 (a slighter lower threshold compared to

Raudenbush and Bryk¹⁶⁴ (p.125), we will treat counselor as a fixed effect. The primary contrast is between groups' difference in change from baseline to month 6 (end of acute treatment through Stage 1 and Stage 2 active treatment). The follow-up contrast at week 26 (12 weeks post-acute treatment) will also be examined in this and in all subsequent analyses. LMMs like the above for the primary outcome will be run for the secondary longitudinal outcomes: CAMS vs. TAU on CCAPS subscales (Depression, Anxiety, Academic Distress, Overall Distress), CGI-I and CGI-S (measured by IE), and cumulative GPA.

AIM 3 analyses will examine the relative effectiveness of switching to a more comprehensive suicide-focused treatment approach (e.g., CC-DBT) among those who do not respond sufficiently to Stage 1 treatments vs. a less intensive suicide-focused approach (e.g., CAMS). This analysis is a comparison of cells C+F (switch to CC-DBT) vs. B+E (switch or continue with CAMS) in Table 8. Both primary and secondary longitudinal outcomes outlined above will be examined using an LMM like that described above, but (a) including only the subset of responders to Phase 1 treatment, (b) defining group as switching to CC-DBT (cells C+F) vs. continuing or switching to CAMS (cells B+E), and (c) using monthly longitudinal outcomes from week 4 to week 24 (7 measurement occasions).

